#### 4.3.1.2. Sustainability of Serum HBsAg and HBV DNA loss (Sustained Virologic Response)

##### ***Definition of estimands***

Estimands supporting the secondary objective of assessing sustainability of serum HBsAg and HBV DNA (Sustained Virologic Response) loss by GSK3228836 for up to 24 weeks off treatment are defined as follows:

- The group of estimands supporting this objective in participants with CHB receiving 300 mg GSK3228836 for 12 weeks (with at least one dose of IP) is the percentage of participants for each variable regardless of completing IP, interruptions in IP or adherence to IP, without the use of PEG-interferon or other immunomodulator therapies. If PEG-interferon or other immunomodulator therapies are used then the participant's outcome will be treated as a non-responder.
- **Variables:**
  - Sustained Virologic Response (HBsAg <LLOQ and HBV DNA <LLOQ) for 24 weeks after the planned end of GSK3228836 treatment
    - HBsAg and HBV DNA from Week 13 to Week 36 will be used to assess sustained virologic response after the planned end of GSK3228836 treatment without the use of PEG-interferon or other immunomodulator therapies.
  - Sustained Virologic Response (HBsAg <LLOQ and HBV DNA <LLOQ) for 24 weeks after the actual end of GSK3228836 treatment
    - HBsAg and HBV DNA for 24 weeks after end of actual treatment will be used to assess sustained virologic response after the actual end of GSK3228836 treatment without the use of PEG-interferon or other immunomodulator therapies.
- **Population Summary:** percentage of participants for each variable.

##### ***Main analytical approach***

Percentages will be summarised and presented for:

- Sustainability of Serum HBsAg and HBV DNA loss (Sustained Virologic Response).

Analysis windows for the post GSK3228836 treatment assessments are defined in Section [6.2.5](#).

If all analysis windows have non-missing response information, a participant's response (Responder or Non-responder) for sustained virologic response after the planned end of GSK3228836 treatment is determined as follows:

- If participant took PEG-interferon or other immunomodulator therapies during 12 week treatment period or 24 week follow-up period then participant is Non-Responder
- Else if participant had sustained virologic response (HBsAg <LLOQ and HBV DNA <LLOQ) for 24 weeks after planned end of GSK3228836 treatment then participant is a Responder.
- Otherwise participant is Non-Responder.

If all analysis windows have non-missing response information, a participant's response (Responder or Non-responder) for sustained virologic response after the actual end of GSK3228836 treatment is determined as follows:

- If participant took PEG-interferon or other immunomodulator therapies during 12 week treatment period or 24 week follow-up period then participant is Non-Responder
- Else if participant had sustained virologic response (HBsAg <LLOQ and HBV DNA <LLOQ) for 24 weeks after actual end of GSK3228836 treatment then participant is a Responder.
- Otherwise participant is Non-Responder.

For participants where sustained virologic response in the absence of PEG-interferon or other immunomodulator therapies cannot be ascertained due to missing data (withdrawal from the study or missing due to other reasons), the participant will be assumed not to have achieved SVR (non-responder imputation).

#### **4.3.1.3. Effect of 12 weeks GSK3228836 on biomarkers and virus-specific antibody responses**

##### ***Definition of estimands***

Estimands supporting the secondary objective of assessing the effect of 12 weeks GSK3228836 on biomarkers and virus-specific antibody responses are defined as follows:

- **Population:** Participants with CHB who receive at least one dose of IP
- **Treatment:** 300 mg GSK3228836 for 12 weeks (also on stable nucleos(t)ide therapy)
- **Intercurrent events:** Discontinuation of, interruption of, adherence to IP will be ignored (treatment policy). For the categorical variable summaries, and continuous variable summaries, PEG-interferon or other immunomodulator therapies will be handled with hypothetical strategy.

##### **- Variables:**

###### **1) Categorical Variables:**

- Achieving HBsAg <LLOQ over time
- Achieving HBV DNA <LLOQ over time
- Achieving HBsAg <LLOQ and HBV DNA <LLOQ over time

- HBe antibody (anti-HBeAg) levels over time
- Categorical changes from baseline in HBsAg (e.g. <0.5,  $\geq 0.5$ ,  $\geq 1$ ,  $\geq 1.5$ ,  $\geq 3 \log_{10}$  IU/mL) over time  
Note: <0.5 category includes subjects with no change or an increase in HBsAg from baseline.
- ALT>3X ULN over time
- HBs antibody (anti-HBsAg) levels (HBs Antibody  $\geq 11.5$  IU/L is HBs antibody positive and HBs Antibody <11.5 IU/L is HBs antibody negative)

- **Population summary:** Percent of participants in each category.

## 2) Continuous Variables:

- Actual values and change from baseline over time for HBsAg and HBV DNA
- HBs antibody (anti-HBsAg) levels over time
- Area under the curve (AUC) for ALT on treatment (12 weeks), during follow up (24 weeks), and on treatment + follow up (36 weeks).

- **Population summary:** mean values and/or mean changes from baseline for each variable

## 3) Time to Event Variable

- Time to First Occurrence of Maximum ALT (ALT must be greater than 3xULN) during 36 weeks ( treatment + follow up)

Time to first occurrence of maximum ALT (first peak in ALT) during 36 week (treatment + follow-up) is defined as time from baseline to the time of first peak in ALT.

Outcome will be assumed missing (Missing At Random) from the timepoint when subjects first receive PEG-interferon or other immunomodulator therapies.

- Time to First Occurrence of Maximum ALT (ALT must be greater than 3xULN) during 12 week on-treatment period

Time to first occurrence of maximum ALT (first peak in ALT) during 12 week treatment period is defined as time from baseline to the time of first peak in ALT (given the peak occurred during 12 weeks of study treatment. See Section [6.2.2](#) for definition of on-treatment period.

Outcome will be assumed missing (Missing At Random) from the timepoint when subjects first receive PEG-interferon or other immunomodulator therapies.

- Time to First Occurrence of Maximum ALT (ALT must be greater than 3xULN) during 24 week follow-up period

Time to first occurrence of maximum ALT (first peak in ALT) during 24 week off treatment period is defined as time from last dose of study treatment to the time of first peak in ALT occurring after study treatment had ended. See Section [6.2.2](#) for definition of post-treatment period.

Outcome will be assumed missing (Missing At Random) from the timepoint when subjects first receive PEG-interferon or other immunomodulator therapies.

- Time to Maximum ALT (ALT must be greater than 3xULN) during 36 weeks (treatment + follow up)

Time to maximum ALT (maximum peak in ALT) during 36 week (treatment + follow-up) is defined as time from baseline to the time of first peak in ALT.

[figure not shown]
For this analysis, taking PEG-interferon or other immunomodulator therapies will be ignored. Participants will be censored at the last record within the specified time period.

**- Population summary:** Turnbull estimate for median Time to Maximum ALT (>3xULN)

Missing data for variables in this group of estimands will be ignored, only available data will be summarized.

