**Table 1 Changes to Protocol Defined Analysis Plan**

Protocol Defined Analysis	SAP Defined Analysis	Rationale for Changes
Section 4.3.1.3, single table presented for:  Time to Event Variable • Time to Maximum ALT (ALT must be greater than 3xULN) during 36 weeks of	Now presenting 4 tables instead of one: 

Summary of Time to First Occurrence of Maximum ALT

	

At the time of writing the protocol, it was expected that only one peak in ALT would be seen. We have since seen on other studies, that more than one peak can occur.

Protocol Defined Analysis	SAP Defined Analysis	Rationale for Changes
treatment + follow up Population summary: Turnbull estimate for median Time to Maximum ALT (>3xULN)	
 
Summary of Time to First Occurrence of Maximum ALT during 12 week treatment period
 
Summary of Time to First Occurrence of Maximum ALT after GSK3228836 treatment
 
Summary of Time to Maximum ALT
 
	
 
The first analysis, is the analysis which was originally intended for the study looking at the first peak.
 
The other analyses reflect our newly updated learning for ALT, since the time of writing the protocol.
 

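### SAP 4.3.1.3: the Time to Maximum ALT analysis is defined by the first ALT peak, so no analysis times the overall maximum from baseline when a later peak is higher

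*SAP*

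**What the plan says.** The protocol (section 9.4.4) has one time-to-event variable in the biomarker group, Time to Maximum ALT over 36 weeks, with ALT required to exceed 3xULN and a Turnbull median as the summary. SAP 4.3.1.3, item 3, replaces it with four analyses, numbered here 1 to 4 in the order listed.

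- Analysis 1, first occurrence of maximum ALT over 36 weeks: "first peak in ALT) during 36 week (treatment + follow-up) is defined as time from baseline to the time of first peak in ALT".
- Analyses 2 and 3, the same idea restricted to the 12-week treatment period and to the 24-week follow-up.
- Analysis 4, Time to Maximum ALT over 36 weeks, with the definition: "maximum peak in ALT) during 36 week (treatment + follow-up) is defined as time from baseline to the time of first peak in ALT". It adds: "For this analysis, taking PEG-interferon or other immunomodulator therapies will be ignored".

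SAP Table 1 explains the change. When the protocol was written, "it was expected that only one peak in ALT would be seen"; other studies have since shown that "more than one peak can occur". It continues: "The first analysis, is the analysis which was originally intended for the study looking at the first peak". The last of the four tables it lists is "Summary of Time to Maximum ALT".

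**The concern.** Analyses 1 and 4 differ in title and in bracketed gloss, but the rule that a programmer would follow is the same in both: stop the clock at the first peak. Table 1 lists analysis 4 as a separate table and ties the additions to multiple peaks, so it was evidently meant to measure something else, namely the time of the highest peak.

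If the rule is followed as written, a participant whose second flare exceeds the first is reported at the earlier date under a title that promises the maximum. The relation between HBsAg suppression and ALT flares is one of the questions in the study's design rationale (protocol 4.2), so the timing of the largest flare matters to a reader of that table.

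A smaller matter sits beside this. Analysis 4 keeps the protocol's variable name but disregards PEG-interferon and other immunomodulator use, whereas the protocol sets outcomes to missing from first use for every variable in this group.

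**Working it through.** The plan gives no figure to reproduce. The check is a comparison of the definitions, followed by two worked cases.

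**Definitions side by side (SAP 4.3.1.3, item 3)**

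| Analysis | Origin | Period | Operative event (>3xULN) | Immunomodulator use |
|---|---|---|---|---|
| 1 | Baseline | 36 weeks | First peak | Missing at random from first use |
| 2 | Baseline | 12 weeks on treatment | First peak in period | Missing at random from first use |
| 3 | Last dose | 24 weeks of follow-up | First peak after treatment | Missing at random from first use |
| 4 | Baseline | 36 weeks | First peak (glossed as maximum peak) | Ignored |

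Rows 1 and 4 agree on origin, period and event. They differ in the last column and possibly in censoring: a sentence on censoring at the last record follows analysis 4 only. If no participant takes an immunomodulator, the two give the same event times.

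**Case A: second, higher peak in follow-up**

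Inputs: chemistry is scheduled on Days 29 and 106 (protocol Tables 2 and 4); the last planned dose is Day 78 (protocol Table 3); follow-up starts 7 days after the last dose (SAP 6.2.2), so on Day 78 + 7 = Day 85. Assumed, not from the documents: a first peak above 3xULN at Day 29 and a higher one at Day 106. Protocol Table 6 places the anticipated start of the ALT flare at Week 5 (Day 29), so taking Day 29 as a peak is a convenience.

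- Analyses 1 and 2: Day 29.
- Analysis 3: 106 − 78 = 28 days after last dose, provided no qualifying follow-up peak came earlier.
- Analysis 4 as written: Day 29. As glossed: Day 106.
- Error in analysis 4: 106 − 29 = 77 days too early.

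**Case B: both peaks on treatment**

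Assumed: a first peak at Day 29 and a higher one at Day 57, also a scheduled chemistry visit (protocol Table 3).

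- Analyses 1, 2 and 4 as written: Day 29.
- Analysis 3: neither peak falls in follow-up.
- Analysis 4 as glossed: Day 57, a difference of 57 − 29 = 28 days. None of the four tables reports this maximum.

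**No error** arises with a single peak, or when the first peak is the highest.

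**Turnbull interval.** The SAP does not say which interval enters the estimate. For a maximum seen at Day 106, with neighbouring visits at Days 92 and 134, the interval could run from the previous visit to the peak visit (106 − 92 = 14 days) or from the previous to the next visit (134 − 92 = 42 days).

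**Population level.** The documents do not say how many participants would have a later, higher peak, so no effect on the Turnbull median can be calculated.

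**Immunomodulator rule.** Protocol 9.4.4 and SAP 1.1 apply a hypothetical strategy to the whole group, including the time-to-event variable. The strategy statement in SAP 4.3.1.3 names only categorical and continuous summaries and is silent on time-to-event. Analyses 1 to 3 follow the protocol; analysis 4 does not. Table 1 lists the move from one table to four but not this difference.

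**The case against.** The strongest reply is that this is a wording slip that corrects itself. The title, the gloss and Table 1 all point to the overall maximum, and one phrase seems to have been carried over from analysis 1. The SAP also leaves detail to an Output and Programming Specification that is not among the documents. The intent is indeed clear. But the defining sentence is the operative rule, no other definition is given, and this section does not refer to that specification for the ALT event. The reply lowers the likelihood of harm; it does not make the text right.

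A reader might infer that later peaks would vanish from the report. The documents do not support that. Analysis 3 can show a first post-treatment peak, timed from last dose, as in Case A. What is missing is the time from baseline to the overall maximum.

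A reader might also infer that the protocol's estimand has been replaced by one with a different immunomodulator rule. That goes too far. Table 1 names analysis 1 as the one originally intended, and analysis 1 keeps the missing-at-random rule. Analysis 4 states its own rule openly, and the silence on time-to-event variables in the strategy statement may mean that the exception was deliberate. These therapies are prohibited (protocol 6.8.2), so few or no participants may be affected. What stands is a consistency gap: the exception conflicts with protocol 9.4.4 and SAP 1.1, and Table 1 does not list it.

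**Conclusion.** The definition of analysis 4 is wrong as written and should be corrected. Followed literally, it gives too early a time for any participant whose later ALT peak is higher than the first, and the right time for everyone else. This rests on reading the defining sentence as the programming rule and on Table 1's statement that more than one peak can occur.

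The 77 and 28 days are illustrations from assumed peak days. They are neither bounds nor an estimate for the study population, and the number of participants affected is unknown. The immunomodulator mismatch is a minor consistency note. The consequence is confined to a descriptive secondary endpoint in a single-arm study without hypothesis testing; the primary endpoint does not depend on it.

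**What to change.** Define analysis 4 as the time from baseline to the participant's highest ALT above 3xULN over the 36 weeks of treatment and follow-up, taking the earliest visit if the highest value is tied. State which visit interval enters the Turnbull estimate.

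For immunomodulator use, choose one of two routes:

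- Apply the missing-at-random rule as in analyses 1 to 3. State how a participant with a qualifying peak before first use is counted, since the overall maximum is then only partly observed.
- Keep the rule that use is ignored, list it in Table 1 as a supplementary analysis, and write the exception into both SAP 1.1 and the strategy statement of 4.3.1.3. Amending only one of these would leave the two in conflict.

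The cost is a redefinition of one or two sentences, plus either a clarifying sentence or a Table 1 entry and two short amendments. No new data are needed.

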#### 4.4. Exploratory Endpoint(s) Analyses

[figure not shown]
CCI

**CONFIDENTIAL**

212602

CCI

CCI

## 4.5. Safety Analyses

The safety analyses will be based on the Safety Analysis Set, unless otherwise specified.

### 4.5.1. Extent of Exposure

Extent of exposure will be summarized using summary statistics. Number of subjects with < 6 weeks,  $\geq$ 6 – 12 weeks exposure will be presented, and the overall duration of exposure will be summarized. Study intervention compliance will be summarized as described in Section 6.1.5.

Number of days of exposure to study drug for each participant will be calculated based on the formula:

Duration of Exposure in Days = Last injection date – First injection date + 1

The cumulative dose will be based on the formula:

Cumulative Dose = Number of Injections (of 150mg) x 150mg

### 4.5.2. Adverse Events

An adverse event (AE) is considered treatment emergent if the AE onset date is on or after treatment start date. If AE start date is completely missing and the end date is on or after

the treatment start date, the AE will be assumed to be treatment emergent. All AE summaries will be based on treatment emergent events unless otherwise specified.

Adverse events will be coded using the latest version of MedDRA coding dictionary, to give a preferred term and a system organ class. These preferred terms and system organ classes will be used when summarising the data. The severity of AEs and SAEs will be determined by the investigator according to the DAIDS grading system Version 2.1 [[National Institute of Allergy and Infectious Diseases. Division of AIDS, 2017](#)], unless specified otherwise in the protocol.

For AEs by maximum grade summary tables, if a participant reports an AE more than once within an SOC/PT, the AE with the most severe intensity will be included in summaries. Relationship to study treatment, as indicated by the investigator, is classified as “not related” or “related”. Adverse events with a missing relationship to study treatment will be regarded as “related” to study treatment.

The following AE summaries will be presented:

1. AEs overview: summarize the number and percentage of participants with any adverse event, AEs related to study treatment, AEs leading to permanent discontinuation of study treatment, withdrawal from the study, any serious adverse events (SAE), SAEs related to study treatment, fatal SAEs and fatal SAEs related to study treatment.
2. All AEs by system organ class (SOC) and preferred term (PT)
3. All AEs by SOC and PT and maximum grade
4. All drug-related AEs by SOC and PT
5. All drug-related AEs by SOC and PT and maximum grade
6. Serious AEs (SAEs) by SOC and PT
7. AEs leading to withdrawal from the study by SOC and PT
8. AEs leading to permanent discontinuation of investigational product by SOC and PT
9. AEs leading to withdrawal from the study by SOC and PT and maximum grade
10. AEs leading to permanent discontinuation of investigational product by SOC and PT and maximum grade
11. Fatal AEs by SOC and PT
12. AEs by overall frequency
13. Non-serious AEs by SOC and PT
14. Non-serious drug-related AEs by overall frequency
15. Serious fatal and non-fatal AEs by overall frequency

Number of participants with AEs will be summarized if it is not specified otherwise.

In summary tables where AEs are presented by SOC, PT, and maximum grade, SOCs will be sorted in descending order of the total incidence then alphabetically, PTs will be sorted in descending order of the total incidence then alphabetically within the SOC.

For completely missing or partial missing AE start date or end date, imputation rules will be applied following the rules stated in Section [6.2.7](#).

Deaths will be listed including primary cause of death.

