### **6.1.4. Prior and Concomitant Medications**

Concomitant medications will be coded using the GSK Drug dictionary. The summary of concomitant medications will be provided by ingredient, i.e., multi-ingredient medications will be summarized for each individual ingredient rather than a combination of ingredients. The summary will be created using ingredient base names, i.e., ingredients with the same base name but different salt will appear under one base name in the summary. Anatomical Therapeutic Chemical (ATC) classifications will not appear in the summary.

A prior medication is defined as any medications that is ended prior to the date of first dose of study drug.

Medications initiated after the first dose of study drug or initiated prior to the first dose of study drug and continued after the first dose of study drug will be counted as concomitant medications. A medication that cannot be determined as prior or concomitant medication due to partially or completely missing start/stop date will be counted as both prior and concomitant medication.

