	Missing start day and month	
If study intervention start date is missing (i.e. participant did not start study intervention), then set start date = January 1.
 
Else if study intervention start date is not missing:
 
 
○ If year of start date = year of study intervention start date, then 
 
▪ If stop date contains a full date and stop date is earlier than study intervention start date, then set start date = January 1.
 
▪ Else set start date = study intervention start date.
 
 
 
 
Else set start date = January 1.
		
	Missing end day	A '28/29/30/31' will be used for the day (dependent on the month and year).		
	Missing end day and month	No Imputation		
	Completely missing start/end date	No imputation		
Concomitant Medications/Medical History	
 
• Partial dates for any concomitant medications recorded in the CRF will be imputed using the following convention:
 
 
 
 Missing start day	 
If study intervention start date is missing (i.e. participant did not start study intervention), then set start date = 1st of month.
 
Else if study intervention start date is not missing:
 	
 
		Missing start day	
If study intervention start date is missing (i.e. participant did not start study intervention), then set start date = 1st of month.
 
Else if study intervention start date is not missing:

Missing start day	
If study intervention start date is missing (i.e. participant did not start study intervention), then set start date = 1st of month.
 
Else if study intervention start date is not missing:
			

Element	Reporting Detail
	
 
○ If month and year of start date = month and year of study intervention start date, then 
 
▪ If stop date contains a full date and stop date is earlier than study intervention start date, then set start date= 1st of month.
 
▪ Else set start date = study intervention start date.
 
 
 
 
Else set start date = 1st of month.

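### The treatment-emergent rule leaves out an adverse event that has no start date and no usable end date, such as one still ongoing

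*SAP*

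**What the plan says.** SAP 4.5.2 sets two conditions under which an AE is treatment-emergent.

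- With a known onset, the event "is considered treatment emergent if the AE onset date is on or after treatment start date".
- With an unknown onset, emergence is assumed from the end date, provided that it does not precede first dose. The sentence opens "If AE start date is completely missing and the end date is on or after".

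The section then fixes the scope of the tables: "All AE summaries will be based on treatment emergent events unless otherwise specified". It sends incomplete dates to 6.2.7: "For completely missing or partial missing AE start date or end date, imputation rules will be applied following the rules stated in Section".

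In the AE part of SAP 6.2.7, the row "Completely missing start/end date" carries the instruction not to impute. So does the row "Missing end day and month". An AE end date lacking only the day is set to the last day of the month. Partial AE start dates are imputed.

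For medications, SAP 6.1.4 resolves the undatable case explicitly, by entering it in each of the two categories: "A medication that cannot be determined as prior or concomitant medication due to partially or completely missing start/stop date will be counted as both".

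**The concern.** An ongoing event has no end date. If its start date is also completely missing, it has nothing to compare with first dose under either condition, and the imputation section declines to supply a date. The cross-reference in 4.5.2 promises a rule for completely missing dates, but the rule it reaches is to do nothing.

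The result is hard to defend on its merits. Of two events with unknown onset, the one that resolved during the study is counted and the one that has not resolved is not, yet being unresolved is no evidence that an event began before treatment. At stake are the AE incidence tables of a study of about 20 participants, where a single participant is visible in a row.

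**Working it through.** No planned figure is in question, so the check is a trace of SAP 4.5.2 and 6.2.7 over the possible states of the two dates.

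| Start date | End date | After 6.2.7 | Status under 4.5.2 |
|---|---|---|---|
| Full, on or after first dose | Any | Unchanged | Treatment-emergent |
| Full, before first dose | Any | Unchanged | Not treatment-emergent |
| Partial | Any | Start imputed | Classified on the imputed start |
| Completely missing | Full, on or after first dose | Unchanged | Treatment-emergent |
| Completely missing | Month and year only | End set to month end | Classified on the imputed end |
| Completely missing | Full, before first dose | Unchanged | Not treatment-emergent, correctly |
| Completely missing | Year only | Neither date imputed | Meets neither condition |
| Completely missing | None (ongoing or missing) | Neither date imputed | Meets neither condition |

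Only the last two rows are a problem. In the year-only row, a calendar year before or after that of first dose would settle the order of events, but the SAP gives no rule for using it. A comparison of full dates would find no date.

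**Direction.** Protocol 8.2.6.1 has AEs before first dose recorded only if they are related to study participation; other occurrences between consent and first dose go to medical history. An event on the AE page with unknown onset is therefore more likely to have started after first dose than before it. Leaving out a true pre-dose event is correct, and leaving out a true post-dose event lowers incidence. No path through the gap raises incidence.

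**Size.** SAP Section 5 plans about 20 participants and at most 24. The AE tables count participants, so each affected participant changes a row by at most:

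- 1/20 = 5.0 percentage points at the planned size;
- 1/24 = 4.2 percentage points at the maximum.

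The change is zero if the participant has another qualifying event in the same preferred term, system organ class or category.

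**After the fix.** With emergence assumed unless the end date shows otherwise, the ongoing row becomes treatment-emergent. The year-only row becomes treatment-emergent unless its year precedes that of first dose. No other row changes.

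**The case against.** The strongest reply is that the case is nearly empty. A completely missing start date means that not even the year is known. AEs are collected only from consent, in a study not expected to exceed 45 weeks. AE review is scheduled at every visit from baseline, monitors verify the case report form against source, and the primary analysis follows database lock. An event whose start month or year is known is handled by the partial-date rules. All of this stands, and it keeps the point minor.

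A reader might also infer four stronger things, which the documents do not support.

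- *That the SAP expressly excludes these events.* It says when an event is assumed treatment-emergent, and is silent otherwise. The exclusion follows from the absence of any other route. The Output and Programming Specification, which is not among the documents, might supply one, but 4.5.2 does not refer to it here.
- *That the rule reverses the SAP's other conventions.* It already assumes emergence on the strength of an end date alone and leaves one corner uncovered. Partial AE start dates move to first dose only when the known month and year (or the year alone) match it and no full stop date is earlier; otherwise they go to the first of the month or 1 January. The medication rule counts an item in two categories, which is not a direct parallel.
- *That every lost event costs 5 points, or that all unresolved events are lost.* The figure is a maximum per affected participant per row. Unresolved events with a full or partial start date are classified normally.
- *That a safety signal could vanish.* AEs of special interest and deaths are listed (SAP 4.5.2 and 4.5.2.1). Low platelet counts, for example, are summarised from dated laboratory results (SAP 4.5.3.1), independently of AE dates.

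The gap itself survives: nothing in either document classifies an AE with no start date and no usable end date.

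**Conclusion.** The point holds as a small drafting gap. An AE with no start date that is ongoing, or whose end date gives only the year, meets neither treatment-emergent condition and, if coded as written, is absent from the default AE summaries. A resolved event with the same unknown start and a usable end date on or after first dose is counted. Any error is towards lower incidence, by at most 5.0 points per affected participant in one row (4.2 with 24 participants).

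This assumes that the programming follows the SAP text with no further rule in the output specification, and that at least one such record survives data cleaning. The documents give no frequency for such records; it should be very low. The study has a single arm and descriptive safety tables, so no between-arm comparison is affected.

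**What to change.** In SAP 4.5.2, replace the sentence on a completely missing start date with: *An AE with a completely missing start date is treatment-emergent unless its end date (full or partial) shows that it ended before the first dose.*

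This covers both the ongoing and the year-only cases, needs no new data, and leaves the imputation table in 6.2.7 as it is. The cost is one sentence and the matching line of code. The downside is that an occasional undated pre-dose event related to a study procedure, for instance the baseline liver aspirate, may be counted as treatment-emergent. Protocol 8.2.6.1 keeps that group small, since only participation-related events before first dose are recorded as AEs.
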